7.5. MISSING DATA

All AEs, unless occurring during an OLFC, real world peanut challenge (RWPC), or DBPCFC, with partial/missing dates and times will be considered TEAEs unless a partial date clearly indicates that it occurred prior to first dose of AR101 in ARC008 or more than 30 days after the last dose of treatment. All therapies with partial or missing dates and times recorded on the Concomitant Medication or Non-Drug Therapy CRF pages will be considered concomitant unless a partial stop date and time clearly indicates it was stopped prior to the first dose of AR101 including parent studies. Start and stop dates will be imputed, to determine TEAEs and concomitant medications, as described below. No imputation will be done for a completely missing stop date or for subjects who did not receive study treatment.

Start dates with a missing day but which have month and year populated will be imputed such that:

- For TEAEs, if the provided month and year match the month and year for that subject's date of first dose of AR101 in ARC008, then the Day 1 date will be used
- For concomitant medications, if the provided month and year match the month and year for that subject's date of first dose of AR101 including parent studies, then the date of first dose of AR101 including parent studies will be used
- In all other cases the 1st of the month will be used with the provided month and year

Start dates with a missing day and month but which have year populated will be imputed such that:

- For TEAEs, if the provided year matches the year for that subject's date of first dose of AR101 in ARC008, then the date of first dose of AR101 in ARC008 will be used
- For concomitant medications, if the provided year matches the year for that subject's date of first dose of AR101 including parent studies, then the date of first dose of AR101 in including parent studies will be used
- In all other cases the 1st of January will be used with the provided year

For TEAEs, start dates that are completely missing will be imputed as the date of first dose of AR101 in ARC008 (Day 1). For concomitant medications, start dates that are completely missing will be imputed as the date of first dose of AR101 including parent studies.

Stop dates will be imputed as follows:

• Missing day with a provided year and month will use the last day of the month

• Missing day and month with provided year will use December 31

If the imputed stop date is greater than the last study date for the subject, then the imputed date will be replaced with the last known subject date.

The reported date of the most recent reaction to peanut on the peanut allergy history CRF page and date of diagnosis of peanut allergy will be imputed when the month or day is missing as follows:

- Missing day is set to 1 if the same year and month as the informed consent date. Otherwise it is set to 15.
- Missing month and day are set to Jan 1 if the same year as the informed consent date. Otherwise it is set to July 1.

Where the severity score of a symptom is missing during a food challenge (OLFC or DBPCFC), the severity score will be imputed as severe.

Where the severity score of an AE is missing, the severity score will be imputed as severe.

Where the relatedness of an AE is missing, the relatedness will be imputed as related to study product.

No imputations will be made for other missing data, unless specified otherwise.

7.6. POOLING

Data pooling will not be performed.

7.7. DATA ADJUDICATION

As the study ended much earlier than originally anticipated some of the locked or frozen data had to be adjudicated by the Nestle Health Science study team. All outcomes of this adjudication are documented in the Site Closure Plan, Adjudication Charter and in Appendix A.

Additional data issues and analysis issues identified during the analysis and how they were handled are captured in separate tracking documents.

8. DEMOGRAPHIC, OTHER BASELINE CHARACTERISTICS

8.1. SUBJECT DISPOSITION AND WITHDRAWALS

Subject disposition and completion status will be summarized for all screened subjects. The number and percentage of subjects who were screened, were screen failures, were included in each analysis population, were in each treatment pathway, were assigned to daily/non-daily dosing regimens, entered each study period, completed all dosing as defined in the protocol, completed the study per protocol, and completed the safety follow-up per protocol will also be summarized.

Reason for early treatment discontinuation, early study discontinuation, and premature discontinuation from follow-up, including due to COVID-19 related reasons, will be summarized as well as whether subjects required follow-up due to chronic/recurrent GI symptoms.

The dates of last study visit, last contact, and study completion/early discontinuation will be listed as well as reason for early treatment discontinuation, reason for early study discontinuation, and reason for premature discontinuation from follow-up. Follow-up status for subjects who required follow-up due to recurrent GI symptoms will also be included in the subject data listings.

Inclusion and exclusion eligibility will be listed separately.

8.2. **PROTOCOL DEVIATIONS**

Major protocol deviations (identified by sponsor review before database lock) will be summarized for the Safety Population. All protocol deviations, as defined in Section 5, will be listed by treatment pathway and subject ID.

8.3. DEMOGRAPHIC AND OTHER BASELINE CHARACTERISTICS

Summary statistics for demographic and baseline characteristics will be provided for the Safety Population by treatment pathway.

Demographic data will include age, age category (1-3 years, 4-17 years, 18 years and older), race, country, ethnicity, sex, body weight, height and body mass index (BMI) where BMI is calculated as [weight (kg)]/[height (cm)/100]². Baseline characteristics include total IgE, ps-IgE, ps-IgG₄, and ps-IgE/IgG₄ ratio. Peanut-specific IgE and IgG₄ components (Ara h 1, Ara h 2, Ara h 3, Ara h 8, Ara h 9) and the corresponding IgE/IgG₄ ratio of each component will also be summarized where available. Baseline SPT mean wheal diameter and asthma history will also be summarized.

Age will be calculated relative to date of informed consent, as follows:

- If the month and day portion of the informed consent date is prior to the month and day portion of the birthdate, age will be calculated as the year of informed consent minus the year of birth, minus one;
- If the month and day portion of the informed consent date is on or after the month and day portion of the birthdate, age will be calculated as the year of informed consent minus the year of birth.

Demographic and baseline characteristic information will be listed by treatment pathway and subject ID for all enrolled subjects. Available demographic data for screening failure subjects will also be listed.

8.4. NON-PEANUT ALLERGY HISTORY

The presence of non-peanut food allergy history and causative allergen types will be summarized for the Safety Population, including the summarization of subjects who have one, two, three, or more than three types of other causative allergens. Additionally, nonfood allergy history and causative allergen types will be summarized for the Safety Population, including the summarization of subjects who have one, two, three, or more than three types of other allergies and other causative allergens. This summary will include non-peanut allergy history from subjects' parent studies (ARC001, ARC003, ARC004, ARC005, ARC007, ARC010, and ARC011). ARC002 non-peanut food and non-food allergy histories were not collected separately and will not be summarized or listed.

All non-peanut food allergy history and non-food allergy history including history collected for parent studies other than ARC002 will be listed by treatment pathway and subject ID.

8.5. NON-ALLERGY MEDICAL HISTORY

Subjects who experience non-allergy medical history events will be summarized for the Safety Population; these data will be presented by system organ class (SOC) and preferred term (PT). This summary will include medical history from subjects' parent studies. Non-allergy medical history for ARC008 will be coded using Medical Dictionary for Regulatory Activities (MedDRA) version 26.0. Non-allergy medical history for parent studies were coded using MedDRA version 18.1 for ARC003, MedDRA version 19.1 for ARC004, ARC007, ARC010, and ARC011, and MedDRA version 21.1 for ARC005. Medical history was not coded for ARC001 and ARC002 and will not be included in the summary of medical history. Medical history including history collected for all parent studies (ARC001, ARC002, ARC003, ARC004, ARC005, ARC007, ARC010, and ARC011) will be listed by treatment pathway and subject ID.

9. ANALYSIS OF SAFETY ENDPOINTS

Safety will be assessed based on extent of exposure, concomitant medications, physical examinations, vital signs, laboratory data and all the safety endpoints defined in Section 3.1.

Unless otherwise noted, safety data will be summarized descriptively, and the Safety Population will be used for all summaries of safety parameters. Safety listings will include all enrolled subjects, sorted by treatment pathway and subject ID.

9.1. ADVERSE EVENTS

TEAEs will be summarized excluding symptoms recorded during the food challenges.

AEs will be classified by severity using the Consortium of Food Allergy Research (CoFAR) grading system for allergic reactions, modified European Academy of Allergy and Clinical Immunology (EAACI) guidelines for anaphylactic reactions, and Common Terminology Criteria for Adverse Events (CTCAE) for all other AEs, all as per Section 8.2.2.1 of the protocol.

If symptoms are recorded as part of an anaphylactic reaction, only the single anaphylactic reaction event will be summarized and not the individual symptoms.

All reported AEs will be classified into SOC and PT using MedDRA version 26.0.

TEAEs are defined as those AEs with onset after the first dose of AR101 in ARC008 and no more than 30 days after the last dose of study drug. Non-TEAEs will be listed by treatment pathway and subject ID; these events will not be summarized. TEAEs will be summarized for the Safety Population by study period as follows:

- Initial Escalation
- Up-Dosing
- Initial and Extended Maintenance
- Overall (Initial Escalation, Up-Dosing, and Initial and Extended Maintenance)

Summaries that are displayed by system organ class and preferred terms will be ordered by descending incidence of system organ class and preferred term within each system organ class. Summaries displayed by preferred term only will be ordered by descending incidence of preferred term. Summaries of the following types will be presented:

• Overall summary of the number of unique TEAEs and TESAEs and subject incidence of TEAEs and TESAEs meeting various criteria;

- Overall summary of the number of unique TEAEs and TESAEs and subject incidence of TEAEs and TESAEs meeting various criteria by total exposure including parent studies;
- Subject incidence of TEAEs by MedDRA system organ class and preferred term;
- Subject incidence of TEAEs by severity grade, MedDRA system organ class, and preferred term;
- Subject incidence of grade ≥ 3 severity TEAEs by MedDRA system organ class and preferred term;
- Subject incidence of TESAEs by MedDRA system organ class and preferred term;
- Subject incidence of TEAEs leading to discontinuation of study product by MedDRA system organ class and preferred term;
- Subject incidence of TEAEs leading to discontinuation of study product by total AR101 exposure including parent studies, MedDRA system organ class, and preferred term;
- Subject incidence of treatment-related AEs by MedDRA system organ class, and preferred term;
- Subject incidence of grade ≥ 3 severity treatment-related AEs by MedDRA system organ class and preferred term;
- Subject incidence of treatment-related AEs leading to discontinuation of study product by MedDRA system organ class and preferred term;
- Subject incidence of TEAEs associated with epinephrine use by MedDRA system organ class and preferred term; and
- Subject incidence of TEAEs associated with accidental/non-accidental non-study product food allergen exposure by MedDRA system organ class and preferred term.

The overall summary of TEAEs and TESAEs will be repeated for the subgroups described in Section 6.3.

At each level of summarization (e.g., any AE, SOC, and PT), subjects experiencing more than one TEAE will be counted only once within each study period. In the summary of TEAEs by severity grade, subjects will be counted once at the highest severity reported at each level of summarization.

AE data will be presented in data listings by treatment pathway, subject ID, and event date. TEAEs for subjects who did not tolerate non-daily dosing in Treatment Pathway 1 and switched to Treatment Pathway 2 will be presented in the data listings. Non-TEAEs, TEAEs, TEAEs identified as the primary reason for early study product discontinuation, TEAEs identified as the primary reason for early study discontinuation, treatment-emergent GI AEs in subjects who discontinued treatment due to GI AEs and had follow-up due to recurrent GI symptoms, treatment-emergent allergic AEs excluding food allergens, and treatment-emergent allergic AEs caused by food allergens will also be presented in separate data listings.

A listing of deaths will also be presented.

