3.2.7 Follow-Up Observation Period (All Treatment Pathways)

The End of Treatment visit will be followed by a 12-month observation period. During observation, management of peanut allergy will be guided by the subject's physician.

ARC008 Protocol Amend 6.0

Observation assessments will be conducted by telephone at 3, 6, and 9 months to enquire about the following:

- Current treatment plan (eg, commercially available product, complete peanut avoidance, use of food equivalents for peanut oral immunotherapy, other investigational immunotherapy, other)
- Events of systemic allergic reactions, EoE, accidental/nonaccidental exposures to food allergens and their outcomes, use of epinephrine, hospitalizations (all causes), emergency department visits (all causes), and SAEs

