9.7 Safety Analyses

All safety endpoints will be summarized using descriptive statistics. Further details will be provided in the SAP.

AEs will be coded based on the Medical Dictionary for Regulatory Activities terminology. Events will be tabulated by system organ classification and preferred term.

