2. STUDY OBJECTIVES

2.1. PRIMARY OBJECTIVE

The primary objective of the study is to describe safety and tolerability during longer-term administration of AR101 and follow-up observation after the last dose of AR101.

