Maintenance	2, 3, and 5	The day following the date of first in- clinic dose of 300 mg during the Up- Dosing period. For subjects who did not enter the Up-Dosing period: the date of first Initial Maintenance Visit.	Date of last dose of study product
Follow-Up Observation	All (1-5)	The day following the date of last dose of study product	Date of Study Exit visit. For subjects without a date of Study Exit visit: the date of study completion.
Overall	All (1-5)	Date and time of first in-clinic or at home dose of treatment in ARC008	Date of Study Exit visit. For subjects without a date of Study Exit visit: the date of study completion.

Table 4Study Period Definitions

- The active treatment period is defined as the time period beginning with the date and time of the first dose of study product and ending with the date and time of the last dose of study product.
- Duration of active treatment period (days) for AR101 is calculated as the date of last dose minus the date of first dose of AR101 plus 1.

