9.2.1. Anaphylaxis

Anaphylactic AEs will be considered AEIs. Anaphylaxis is defined by a number of signs and symptoms that occur alone or in combination within minutes up to a few hours after exposure to a provoking agent. The severity of the reaction will be assessed according to the EAACI system for grading the severity of anaphylactic reactions (Muraro, 2007).

All reported anaphylactic reaction episodes will be listed by treatment pathway and subject.

Each anaphylactic reaction will be identified by the following triggers:

• Study product/Investigational product (IP)

- Peanut or peanut-containing food
- Other food allergen
- Medication
- Insect sting
- Environmental allergen(s)
- Other
- Unknown

Treatment-emergent anaphylactic reactions include anaphylactic reactions that occur after first dose of AR101 in ARC008 through 30 days after last dose of study product, but excluding anaphylactic reactions that occur during or related to a food challenge. Treatment-emergent anaphylactic reactions will be summarized in the Safety Population separately for the following study periods:

- Initial Escalation
- Up-Dosing
- Initial and Extended Maintenance
- Overall (Initial Escalation, Up-Dosing, and Initial and Extended Maintenance)

Summaries of each study period will include:

- The number of anaphylactic reactions.
- The number of anaphylactic reactions by trigger, study product, peanut or peanutcontaining food, other food allergen, medication, insect sting, environmental allergen, other and unknown.
- Incidence of subjects experiencing an anaphylactic reaction by number of episodes, subjects experiencing an anaphylactic reaction by severity using modified EAACI guidelines, subjects experiencing an anaphylactic reaction that was a SAE, subjects experiencing an anaphylactic reaction that required epinephrine use, the location of epinephrine episodes (home or study site), and the individual symptoms involved.

The above summary will be produced for all treatment-emergent anaphylactic reactions, all treatment-emergent anaphylactic reactions by total AR101 exposure including parent studies, and for treatment-related anaphylactic reactions. Anaphylactic reactions will also be listed by treatment pathway, subject ID, and episode date.

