9.2.3. Accidental and Non-accidental Food Allergen Exposures

An accidental food allergen exposure is any known or suspected exposure to a food to which the subject is allergic, including peanut, whether or not it results in an AE. A non-accidental food allergen exposure is an intentional exposure to a food to which the subject is allergic, including peanut, whether or not it results in an AE.

The non-serious AEI form will be completed for each of these events, in addition to events where consumption of peanut without a reaction occurs, unless the accidental/non-

accidental food ingestion safety event meets the definition of an SAE as defined in Section 8.1.3 of the protocol, in which case the SAE form will be completed.

If an accidental/non-accidental food allergen exposure does not result in an AE, no assessment of severity, seriousness, or relatedness is required. Treatment-emergent food allergy episodes include food allergy episodes that occur after first dose of AR101 in ARC008 through 30 days after last dose of study product, but excluding food allergy episodes that occur during or related to a food challenge.

These treatment-emergent food allergy episodes will be summarized by study period:

- Initial Escalation
- Up-dosing
- Initial and Extended Maintenance
- Overall (Initial Escalation, Up-Dosing, and Initial and Extended Maintenance)

For each period, the number of subjects experiencing any food allergy episode, the number of subjects experiencing a food allergy episode in response to peanut (or non-peanut), the number of subjects experiencing an accidental (or non-accidental) food allergy episode, the number of episodes of each (peanut-related, non-peanut related, accidental, and non-accidental) experienced per subject, and the total number of food allergy episodes (peanut-related, non-peanut related, non-peanut related, accidental) will be summarized. In addition, the number of episodes considered SAEs, those that required treatment, and those that required epinephrine use will also be summarized.

All reported food allergy episodes will be listed by treatment pathway and subject.

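### Apart from medication use, safety events starting more than 30 days after the last dose are listed but not tabulated, although follow-up is part of the primary objective

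*SAP*

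**What the plan says.** The primary objective (SAP 2.1, matching Protocol Section 2) is to "describe safety and tolerability during longer-term administration of AR101 and follow-up observation after the last dose of AR101". For the follow-up part, Protocol 3.2.7 schedules telephone assessments at months 3, 6 and 9 that ask about "Events of systemic allergic reactions, EoE, accidental/nonaccidental exposures to food allergens and their outcomes, use of epinephrine", and also about hospital admissions, emergency visits and SAEs. The Study Exit visits in Protocol Section 7 repeat the key-events review at month 12. Protocol 9.7 states: "All safety endpoints will be summarized using descriptive statistics".

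SAP 9.1 defines a TEAE as an event with onset after the first ARC008 dose and within 30 days of the last dose. Everything else falls under this sentence: "Non-TEAEs will be listed by treatment pathway and subject ID; these events will not be summarized". SAP 9.2.1 summarizes "anaphylactic reactions that occur after first dose of AR101 in ARC008 through 30 days after last dose of study product", and SAP 9.2.3 summarizes "food allergy episodes that occur after first dose of AR101 in ARC008 through 30 days after last dose of study product". The adverse-event-of-interest summary in SAP 9.2 covers treatment-emergent events only. Deaths are listed.

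Table 4 in SAP 7.4 defines a Follow-Up Observation period that begins on "The day following the date of last dose of study product" and ends at Study Exit. It runs the Overall period from first dose to Study Exit. SAP 9.1 instead defines it as "Overall (Initial Escalation, Up-Dosing, and Initial and Extended Maintenance"), which contains no follow-up.

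**The concern.** A 30-day window is a normal way to define on-treatment safety. Here, though, safety after the last dose is also part of the primary objective, and data are collected for it prospectively. If the SAP is followed as written, the report gives no follow-up frequency after day 30 for anaphylaxis, EoE, food-allergen exposures, hospital admissions, emergency visits or SAEs. A reader would have to count them from listings.

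EoE is the most exposed endpoint. Its frequency is a primary safety endpoint (SAP 3.1), yet the SAP text names no EoE summary, so it can be read only from treatment-emergent tables. Section 13 of the SAP names several endpoints that were reduced to listings; this restriction is not among them.

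**Working it through.** No sample size, power or alpha is involved, and the plan gives no figure to reproduce. The check is an inventory of planned safety outputs by time window, followed by simple arithmetic.

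**1. Which safety-event summaries include onset after day 30?**

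| Output (SAP section) | Onset after day 30 |
|---|---|
| TEAE and TESAE tables (9.1) | Listed only |
| Deaths (9.1) | Listed only |
| Adverse events of interest (9.2) | Not in the summary |
| Anaphylaxis (9.2.1) | Listed only |
| Food-allergen episodes (9.2.3) | Listed only |
| EoE | No specific summary named |
| Hospital admissions and emergency visits in follow-up | No table described |
| Concomitant medication (9.12) | Included; drugs started after the last dose count |
| Rescue medication, Overall row (9.12) | Included; no time limit |

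No event summary includes onset after day 30. The medication tables are the exception. The rescue-medication Overall row pools use during dosing, food challenges and follow-up, so it gives no follow-up frequency of epinephrine use. Disposition and the Study Exit immunology and skin-prick summaries also reach follow-up, but they are not safety-event tables.

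**2. How much follow-up time is that?** Inputs: follow-up of T days, with 1 month = 365.25/12 days (SAP 7.4), and the 30-day window (SAP 9.1). Share outside the event tables = (T − 30)/T.

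- 12 months: (365.25 − 30)/365.25 = 335.25/365.25 = 91.8%
- 6 months: (182.6 − 30)/182.6 = 152.6/182.6 = 83.6%
- 3 months: (91.3 − 30)/91.3 = 61.3/91.3 = 67.1%

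The shorter durations are assumptions. SAP 7.7 says the study ended well before it was expected to, but it does not say that follow-up was cut short. The four key-event reviews fall at about days 91, 183, 274 and 365, all after day 30.

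**3. Where do events on days 1 to 30 after the last dose go?** In Table 4, Maintenance ends on the date of the last dose, and Follow-Up Observation starts the next day. A TEAE on day 10 after the last dose is therefore in Follow-Up Observation, for which SAP 9.1 has no column. Under the Table 4 definition of Overall it is still counted there. Under the SAP 9.1 definition, the sum of three dosing periods, it is counted nowhere. On that second, literal reading the untabulated share is 365/365 = 100%.

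**4. Could EoE be missed?** Protocol 8.1.4.2 calls for gastroenterology referral if chronic or recurrent GI events have not fully resolved 6 weeks (day 42) after stopping AR101, or if symptomatic therapy cannot be stopped by 12 weeks (day 84). Both points are after day 30, although earlier referral is allowed. A case dated at diagnosis could fall outside the tables, while a case dated at first symptom might not. The documents do not say which date is used.

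**The case against.** The strongest objections, and what stands of each:

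- **Protocol 9.7 leaves further detail to the SAP, and the endpoints state no time window.** Correct. The gap is therefore clearest against the objective rather than as a breach of 9.7. Delegating detail does not remove the follow-up part of the objective.
- **Calendar share is not event share.** This stands. An event on day 20 that is first reported at month 3 is still a TEAE and is tabulated. Every subject also has a telephone contact at least 14 days after the last dose or food challenge, and adverse events with partial or missing dates default to TEAE (SAP 7.5). None of this creates a summary of later events.
- **The 100% figure needs a reading that defeats the SAP's own TEAE definition.** It is conditional on the literal wording of SAP 9.1 and is not the expected outcome. The contradiction with Table 4 remains.
- **The table shells were not supplied, and SAP Section 9 summarizes safety data by default.** The default gives way to SAP 9.1 for adverse events. For hospital admissions, emergency visits and other key events not recorded as AEs, the SAP describes no table, though the shells might contain one.
- **Follow-up mixes subjects on commercial product, food equivalents, other immunotherapy and avoidance.** True, and it limits attribution. The objective is descriptive, however, and current treatment plan is collected.
- **Nothing is hidden.** Late adverse events, deaths, anaphylaxis and food-allergy episodes are all listed. Listings do not give a frequency.

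**Conclusion.** The point holds and should be fixed. Part of the primary objective has no planned event frequency after day 30, because of an explicit rule and not merely because detail is missing. The untabulated share of follow-up time is about 92% for a completed 12 months, and 84% or 67% if follow-up stops at 6 or 3 months.

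The number of events affected cannot be estimated from the documents; for EoE it may be zero. Because the SAP reports subject incidence, leaving out late events can only lower the cumulative figures, so any error favours the product. A rate per person-year could move either way. The conclusion rests on the SAP text and assumes that the table shells add no follow-up summary.

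**What to change.** - Add a Follow-Up Observation column using the Table 4 dates, with subjects entering follow-up as the denominator and person-years shown. Cover the key events in Protocol 3.2.7: systemic allergic reactions, EoE, food-allergen exposures, epinephrine use, hospital admissions, emergency visits and SAEs. A split by current treatment plan is optional.
- Leave the TEAE window as it is. A full AE table for months 2 to 12 is not needed, because Protocol 8.2.1 requires general AE recording only for at least 14 days after the last dose or food challenge, or until ongoing events resolve or stabilize.
- Summarize EoE from first ARC008 dose to Study Exit, and state whether onset is dated at first symptom or at diagnosis.
- Use one definition of Overall in Table 4 and SAP 9.1, 9.2.1 and 9.2.3, and state which column holds TEAEs from days 1 to 30 after the last dose.
- Declare the change in Section 13 or, since SAP 1.1 records that the database is locked, report it as a documented post-hoc addition by the route in SAP 6.1.

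The cost is a few extra tables and shells built from data and period flags that already exist. The additions carry a post-hoc label, and the reported frequencies may be slightly less favourable.
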